6 INTRODUCTION

Generalized anxiety disorder (GAD) is one of the most frequently occurring childhood anxiety disorders¹. In the United States, an estimated 2.2% of adolescents (aged 13 through 18 years) had GAD, with an estimated 0.9% having severe impairment based on data published in 2010. The prevalence of GAD among adolescents was higher for females (3.0%) than for males (1.5%)².

An anxiety disorder such as GAD in children and adolescents increases the risk for substance abuse and suicidal ideation and suicide attempts, and also increases the risk for anxiety or depressive disorders in adulthood^{3,4,5}. However, anxiety disorders are often untreated in children and adolescents⁶.

There is increasing evidence to suggest that selective serotonin reuptake inhibitors (SSRIs) are effective treatments for youth with GAD and are generally well tolerated⁷.

Escitalopram, the S-enantiomer of racemic citalopram, is an SSRI primarily responsible for the serotonin reuptake inhibition produced by citalopram. Escitalopram binds preferentially to the serotonin transporter and has very low or no affinity for neurotransmitter receptors or for the dopamine and norepinephrine transporters. The mechanism of antidepressant action of escitalopram is presumed to be linked to potentiation of serotonergic activity in the central nervous system resulting from its inhibition of central nervous system neuronal reuptake of serotonin (5-hydroxytryptamine).

Five clinical studies evaluating the efficacy and safety of escitalopram in adult patients with GAD have been completed. Three of the 5 studies were placebo-controlled; one was an open-label extension study; and one was a relapse-prevention study. The efficacy of escitalopram in the acute treatment of GAD was demonstrated in the three, 8-week, flexible-dose, placebo-controlled studies. In all 3 studies, escitalopram showed statistically significant greater mean improvement compared to placebo on the Hamilton Anxiety Scale. Results from the relapse-prevention study showed that treatment with escitalopram at 20 mg/day significantly reduced the risk of relapse of GAD.

The most commonly observed adverse reactions in the placebo-controlled double-blind studies in adult escitalopram patients (incidence of approximately 5% or greater and approximately twice the incidence in placebo patients) were nausea, ejaculation disorder (primarily ejaculatory delay), insomnia, fatigue, decreased libido, and anorgasmia.

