8.3.5 Removal of Subjects From the Study

A subject may voluntarily withdraw or be withdrawn from the study at any time for reasons including, but not limited to, the following:

- Withdrawal of consent
- Use of non-permitted concurrent therapy
- Noncompliance with the study drug or study schedule
- Lost to follow-up
- Adverse event
- Investigator request
- Intercurrent illness
- Protocol deviation
- Pregnancy
- Sponsor request
- Lack of efficacy
- Due to the COVID-19 pandemic
- Death

Subjects who do not complete the study will not be replaced.

Subjects are free to withdraw from the study at any time without providing reason(s) for withdrawal and without prejudice to further treatment. The reason(s) for withdrawal will be documented in the electronic case report form (eCRF).

Subjects withdrawing from the study will be encouraged to complete the same final evaluations as subjects completing the study according to this protocol, particularly

CONFIDENTIAL

safety evaluations. The aim is to record data in the same way as for subjects who completed the study.

Subjects who withdraw early from the study should complete the End of Treatment Visit and enter the 1-week down taper period.

Subjects should be monitored for the following symptoms when discontinuing treatment: dysphoric mood, irritability, agitation, dizziness, sensory disturbances (eg, paresthesias such as electric shock sensations), anxiety, confusion, headache, lethargy, emotional lability, insomnia, and hypomania. A gradual reduction in dose rather than abrupt cessation is recommended, whenever possible.

Reasonable efforts will be made to contact subjects who are lost to follow-up (eg, 3 attempts to contact the subject by telephone/letter). These efforts must be documented in the subject's file.

The sponsor has the right to terminate the study at any time in case of serious adverse events (SAEs) or if special circumstances concerning the investigational product or the company itself occur, making further treatment of subjects impossible. In this event, the investigator(s) will be informed of the reason for study termination.

Pregnancy

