11.5.1.1.1 Estimand for the Primary Efficacy Analysis

The following describes the estimand approach for the primary efficacy analysis described in ICH E9 (R1) (2017)¹⁷.

Target Population

As noted above in [Section 11.5](#), the target population is the mITT population.

Variable

The variable is the same as the definition of the primary efficacy analysis described in [Section 11.5.1.1](#).

Accounting for Intercurrent Events

The primary analysis will treat measurements after study withdrawal as missing in the MMRM modeling, leading to an estimate of the treatment effect while on treatment. The impact of the missing at random assumption of MMRM will be assessed using 2 different approaches. The first will be a simple last observation carried forward (LOCF) approach. The second will be a sensitivity analysis using a pattern-mixture model. The details of this sensitivity analyses will be provided in detail in the SAP.

Population-level Summary

The population-level summary for the primary endpoint is the difference in primary variable means between the escitalopram group and placebo, while remaining on the study treatment.

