9.1 PRIMARY EFFICACY PARAMETER

9.1.1 Primary Objective Estimand

The estimand used to address the primary objective "To determine efficacy of escitalopram relative to placebo in the acute treatment of children (aged 7 through 11 years) and adolescents (aged 12 through 17 years) who meet criteria for GAD as defined in the Diagnostic and Statistical Manual of Mental Disorders" is defined by the following:

• Population:

Page 24 of 53

- The target population is children (aged 7 through 11 years) and adolescents (aged 12 through 17 years) with GAD and who satisfy the inclusion and exclusion criteria as specified in the protocol.
- The analysis population is mITT population defined in section 5.4.

Variable:

O Change from baseline to Week 8 in PARS severity. The PARS severity score is derived by summing 5 of 7 severity/impairment/interference items (2, 3, 5, 6, and 7).

Intercurrent events:

- To evaluate the efficacy at Week 8 in the mITT population, participants are assumed to adhere to the assigned treatment for the duration of the study. As a result, data after the discontinuation from the study treatment due to all reasons will not be included in the primary analysis and they will be assumed as missing at random.
- For the sensitivity analyses of primary parameter, the LOCF approach and pattern-mixture model approach will be utilized to impute the missing value. The details are provided in Section 10.1.2.
- Population-level summary:
 - The change from baseline of PARS severity score at Week 8 in subjects treated with escitalopram compared to the change from baseline of PARS severity score at Week 8 in subjects treated with placebo

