For the LOCF approach, only the postbaseline PARS severity score for GAD will be imputed; individual item scores will not be carried forward to derive the PARS severity score. Baseline total score will be carried forward only for the missing scores immediately after baseline. If all the postbaseline values are missing, the baseline value will not be carried forward. The LOCF approach is based on an analysis-of-covariance (ANCOVA) model including treatment group and pooled study center as factors and baseline PARS severity score as a covariate

Another sensitivity analysis using a pattern-mixture model approach based on non-future dependent missing value restrictions (Kenward et al., 2003) will be performed to assess the robustness of the primary MMRM results to the possible violation of the missing-at-random assumption. The details of this sensitivity analysis are as follows:

The pattern for the pattern-mixture model will be defined by the subject's last visit with an observed value. The observed PARS severity score at a visit is assumed to have a linear relationship with the subject's prior measurements. The missing values will be imputed under the assumption that the distribution of the missing observations differs from that of the observed only by a shift parameter value Δ . The dataset with missing values imputed will be analyzed using an analysis of covariance (ANCOVA) model with treatment group and pooled study center as factors and baseline PARS severity score as a covariate for between–treatment group comparisons at Week 8. The imputation of missing values and the analysis will be performed multiple times and the inference of this sensitivity analysis will be based on the combined estimates using the standard multiple imputation technique. The shift parameter values Δ for the multiple imputation will start at 0 and increase by 1 to 6 or until a tipping point is reached (ie, the p-value switches from ≤ 0.05 to ≥ 0.05), whichever is higher.

Page 26 of 53

More details of the proposed pattern-mixture model approach (e.g., the models for the pattern-specific identifiable densities and the unidentified conditional distributions, the shift parameter Δ , and the multiple imputation algorithm) are provided in Appendix I to this SAP.

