13.0 BLINDED INTERIM ANALYSIS

A blinded interim analysis will be conducted when approximately 75% of randomized subjects have either completed the study or discontinued from the study. The blinded interim analysis is to obtain an estimate of the pooled standard deviation of the change from baseline in the PARS score to Week 8 of the double-blind acute treatment period. The sample size will be re-estimated using simulation in the same manner as the original sample size as described in Section 14 using the estimated pooled standard deviation and dropout rate from the blinded interim analysis. If the estimated pooled standard deviation is larger than the assumed pooled standard deviation due to assumption deviation as well as COVID-19 remote visits or dropout rate is increased, the sample size in placebo and escitalopram treatment groups may be increased to ensure an adequate power. However, due to the difficulties in recruiting pediatric subjects with GAD, the number of subjects in each treatment arm will be capped at 160.

As the sample size re-estimation requires only the pooled standard deviation and dropout rate to be updated, all data and personnel will remain blinded for the interim analysis. Randomization code will not be released for the sample size re-estimation. There are no potential unblinding issues in the sample size re-estimation. As this is a blinded re-estimation, there is no impact on the overall Type I error rate of the study.

SAP SCT-MD-60 Allergan

Page 40 of 53

14.0 DETERMINATION OF SAMPLE SIZE

The sample size estimate was constructed using a simulation approach as described in Lu K. (2012).

The primary efficacy parameter is the change from baseline to Week 8 of the double-blind acute treatment period in PARS total score. To detect an effect size (treatment group difference of 2.30 units relative to pooled standard deviation of 5.79) of 0.39, a sample size of 128 subjects in the escitalopram treatment group and 128 subjects in the placebo group will provide 85% power based on an MMRM model using simulation method. The simulation assumed a correlation of 0.7 between the repeated measures, and a common dropout rate of 14%, based on historical data of escitalopram in pediatric subjects.

SAP SCT-MD-60 Allergan

Page 41 of 53

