Note that the two distributions only differ by a shift (Δ) parameter. When $\Delta = 0$, the missing value y_s in Pattern s-l is imputed based on the distribution of all observed data up to Visit s, as a result, leading to missing at random (MAR) missingness. When $\Delta \neq 0$, (8) will introduce a scenario of MNAR. The similar idea was also presented in the recent publication "The Prevention and Treatment of Missing Data in Clinical Trials" by the National Academies Press. The selection of the plausible values for the shift parameter (Δ) is discussed in Section 3 of this appendix.

Note that per recommendation in Wang and Daniels (2011), only the observed data within pattern is assumed to be multivariate normal. The observed data distribution can be expressed in terms of the marginal distribution of baseline measurement and the conditional distributions of postbaseline measurements given earlier measurements. Assuming that these distributions are normal, the linear regression of each observation on prior observations will yield least-squares estimates of model parameters that can be utilized for independent posterior draws of model parameters for observed data. Multiple imputation approach will be used to estimate the overall mean at the final time point.

Page 55 of 53

2. Imputation Procedure

All the missing data will be imputed to create complete datasets, then statistical analysis can be performed using appropriate techniques such as ANCOVA. The imputation can accommodate MNAR missing data mechanisms, based on the theory discussed in the previous section.

The model parameters for each dropout pattern, i.e., the mean, variance and proportions of observations in each pattern, are drawn from their posterior distributions prior to the imputation of missing data for a single imputation.

The details of imputation within a pattern, say Pattern t, are as the following:

Step 1. Impute the first missing value v_{t+1} for each subject in Pattern t (t = 1, ..., T-1):

- a. Compute estimates of mixture probabilities $\lambda_{s-l,j}$ in (7) with s = t+1 given the posterior draw of proportions of observations in each pattern and the posterior draw of regression parameters for the observed data.

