- b. Draw a random integer from $\{s, ...T\}$ to index a component distribution on the right hand side of (6), using mixture probabilities obtained in a). Draw y_{t+1}^* from the identified component normal distribution. Impute the missing y_{t+1} as $\widetilde{y}_{t+1} = y_{t+1}^* + \Delta$.

Step 2. Impute the rest of the missing values of $y_{t+2}, y_{t+3}, ..., y_T$ for subjects in Pattern t:

Starting with imputation for y_{t+2} , first, similar to Step 1, draw y_{t+2}^* from the normal mixture (6) based on the observed $y_1,...,y_t$ and the already imputed \tilde{y}_{t+1} for the subject.

Then the missing y_{t+2} is imputed as $\widetilde{y}_{t+2} = y_{t+2}^* + \Delta$ with probability δ_{t+1} and as $\widetilde{y}_{t+2} = y_{t+2}^*$ with probability $I - \delta_{t+1}$, where the mixture probability $\delta_{t+1} = \omega_{t+1,t+1}$ is obtained from (4) given the posterior draw of proportions of observations in each pattern and the posterior draw of regression parameters for the observed data.

Missing values of y_{t+3} through y_T can be imputed similarly as y_{t+2} .

To summarize, the imputations of y_{t+1} through y_T is done recursively within each Pattern t (for all t = 1,..., T - 1) to create a complete dataset after imputation is done for all patterns with missing values.

Page 56 of 53

The above imputation procedure is applied to all subjects in each missing data pattern to create a single imputed data set. Repeating the process of drawing parameters from the posterior distribution and imputing missing data given the posterior draw m times will yield m imputed data sets. The observed or imputed values at the final data point are averaged to obtain the overall mean estimate for each imputed data set, and the multiple imputation estimate is obtained by averaging the estimates across m imputations.

In this sensitivity analysis, m is set to equal to 20. The value of m is discussed in the context of imputation efficiency in standard multiple imputation theory (Rubin, 1987, p. 114), and m = 20 would provide at least 96% of relative efficiency as compared with using an large number of imputations (SAS/STAT User's Guide, p. 3796).

3. Determination of the Shift Parameter Values

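### The tipping-point analysis applies one shift to both arms, so with similar dropout it barely tests the primary result; add an escitalopram-only or arm-specific shift

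*SAP*

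**What the plan says.** SAP Section 9.1.1 states that "data after the discontinuation from the study treatment due to all reasons will not be included in the primary analysis" and treats those data as missing at random. Section 9.1.2 plans two checks on that assumption: LOCF, and a pattern-mixture model with multiple imputation. In the second, "the distribution of the missing observations differs from that of the observed only by a shift parameter value" Δ. The shift starts at 0 and rises in steps of 1 to 6, or to the tipping point if that is higher.

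Appendix I gives the algorithm. Equations (1) to (8) and imputation Steps 1 and 2 carry no treatment index, and patterns are defined by the last observed visit. "The above imputation procedure is applied to all subjects in each missing data pattern to create a single imputed data set". Part 3 of the appendix calls Δ a common shift and defines it by contrasting subjects who drop out with those who stay. Treatment enters only in the ANCOVA fitted after imputation. Setting Δ = 0 is described as "leading to missing at random (MAR) missingness".

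SAP Section 14.0 sizes the trial under "a common dropout rate of 14" per cent. Protocol Section 11.5.1.1.1 defers the specification: "The details of this sensitivity analyses will be provided in detail in the SAP".

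**The concern.** A tipping-point analysis should show how badly the drug's dropouts would have to do before the result is lost. When the same Δ is added in both arms and similar shares are imputed, the shifts cancel in the treatment difference. Raising Δ then changes only the standard error, and the tipping point marks where added variance removes significance. A large value would look like strong robustness without testing an unfavourable departure on escitalopram. If placebo has more missing data, a larger Δ increases the apparent benefit.

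Unequal departures cannot be ruled out in advance. Protocol Section 8.3.5 lists both adverse events and "Lack of efficacy" among the reasons for withdrawal, and these need not fall evenly across the arms or carry the same prognosis.

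A second gap affects the anchor of the analysis. The SAP does not say whether the imputation regressions are fitted by arm or include treatment, so Δ = 0 may not correspond to the primary missing-at-random analysis.

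**Working it through.** **Inputs (SAP Section 14.0 and Appendix I).** Difference 2.30; SD 5.79; 128 per arm; correlation 0.7; dropout 14% in each arm; m = 20 imputations. PARS is scheduled after baseline only at Weeks 2 and 8, so I assume each imputed subject receives the full Δ at Week 8. Splits other than 14%/14% are illustrative.

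**The plan's power.** The two-visit MMRM variance is 2·SD²·[ρ²/n(Week 2) + (1−ρ²)/n(Week 8)]. With 128 and 110 subjects per arm, 2 × 33.52 × (0.49/128 + 0.51/110) gives SE 0.753 and power 86.3%. With 119/110 it is 85.1%, and with 115/110 it is 84.6%. The stated 85% is reproduced.

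**Effect of Δ.** Let pE and pP be the imputed shares on escitalopram and placebo.

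- Common shift: estimate = 2.30 − Δ(pE − pP)
- Escitalopram-only shift: estimate = 2.30 − Δ·pE
- Each shifted arm adds p(1−p)Δ²/n to the variance.
- Imputation adds (1 + 1/20) × [5.79²(1−0.7²)/n] × Σ p/(1−p), summed over the two arms.

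**At 14%/14%.**

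- Δ = 0: variance = 2 × 33.52/128 + 1.05 × 0.0435 = 0.5695, so SE 0.755 and p = 0.0023.
- Common Δ = 6: the estimate stays 2.30. Variance = 0.5695 + 2 × 0.14 × 0.86 × 36/128 = 0.637, so SE 0.798 and p = 0.0040.
- Escitalopram-only Δ = 6: 2.30 − 0.84 = 1.46. Variance = 0.5695 + 0.0339 = 0.603, so SE 0.777 and p = 0.060.

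**Across missing shares** (normal p-values; tipping point is the first integer Δ with p > 0.05):

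| Imputed, escitalopram/placebo | Common, Δ = 6 | Common tips at | Escitalopram-only, Δ = 6 | Escitalopram-only tips at |
|---|---|---|---|---|
| 14%/14% of 128 | 2.30, p 0.004 | 21 | 1.46, p 0.060 | 6 |
| 10%/18% of 128 | 2.78, p 0.0005 | none up to 200 | 1.70 | 8 |
| 18%/10% of 128 | 1.82, p 0.023 | 9 | 1.22 | 5 |
| 10%/10% of 128 | 2.30 | 25 | 1.70, p 0.026 | 8 |
| 5/115 in each arm (4.3%) | 2.30, p 0.004 | 33 | 2.04, p 0.009 | 16 |

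The last row takes the protocol's figure of about 115 evaluable per arm with about 110 reaching Week 8 (0.86 × 128).

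**A smaller observed effect.** With 1.80 observed at 14%/14%, the tipping points are 13 (common) and 3 (escitalopram-only).

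**Simulation checks.** Both used multiple imputation with treatment in the imputation model, m = 20 and a true difference of 2.30, at 14%/14%.

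- 400 trials: significant in 86% at Δ = 0; at Δ = 6, 84% common and 47% escitalopram-only.
- 1,500 trials (assumed Week 2 effect 1.15): 84.6% at Δ = 0; at Δ = 6, 82.1% common and 43.3% escitalopram-only.

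In the second set, leaving treatment out of the imputation model gave a mean estimate at Δ = 0 of 2.08, against 2.26 with it.

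**The case against.** The strongest reply is about size. Dropouts with no post-baseline PARS leave the mITT and are never imputed, so the imputed share may be well below 14%. At 5 of 115 per arm, an escitalopram-only Δ of 6 still leaves p = 0.009. Even at 14%, Δ = 6 exceeds one SD. Removing the whole 2.30 benefit from every imputed escitalopram subject gives 2.30 − 0.14 × 2.30 = 1.98, p = 0.009. All of this stands and limits the effect when 2.30 is observed. It does not remove the defect: the imputed share is unknown in advance, a smaller observed effect tips much sooner, and the two tipping points differ about twofold even at 4.3%.

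The case for unequal dropout is soft. The protocol introduction's "approximately twice the incidence in placebo patients" is part of the rule for selecting which adult reactions to list and says nothing about withdrawals. If escitalopram does lose more subjects, the common shift already works against it. Both points are fair. But the cancellation under equal dropout needs no such rationale, and a robustness check should not depend on which arm happens to lose more.

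LOCF is a second planned check, but it has no arm-specific penalty that can be varied. The word common in Appendix I may refer to visits only, yet no arm-specific value appears anywhere. Finally, some early-termination scores may fall in the Week 4, 6 or 8 windows, so fewer subjects, or less than the full Δ, might be shifted at Week 8. That would shrink the figures but not undo the cancellation when the arms have similar missingness patterns.

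**Conclusion.** The concern holds. As written, the analysis varies the missing-at-random assumption equally in both arms. Under the plan's own equal dropout the estimate cannot move, and tipping comes only from variance inflation. At 14% imputed per arm and 2.30 observed, the SAP's version tips at Δ = 21; an escitalopram-only version tips at 6, inside the 0 to 6 range the SAP always runs. With 10% missing on escitalopram and 18% on placebo, the common shift raises the estimate to 2.78.

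These sizes rest on the both-arm reading of Appendix I, the full Δ reaching Week 8, and the assumed missing shares. The contrast weakens as fewer mITT subjects lack Week 8. The primary test is unaffected, but this check should be repaired before unblinding.

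**What to change.** In SAP Section 9.1.2 and Appendix I:

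- State which arm or arms receive Δ.
- Add an analysis that applies Δ to escitalopram dropouts with placebo imputed at Δ = 0, or a two-way grid of arm-specific values. The common-Δ run can stay as one line of that grid.
- State that the imputation regressions are fitted by arm or include treatment, so that Δ = 0 corresponds to the primary missing-at-random analysis.
- Keep the mITT population.

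The cost is SAP wording and a small programming change. The protocol leaves these details to the SAP, so population, primary test, alpha and sample size do not change. The downside is that the reported tipping point may be less favourable.

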10.1.1.4 Global COVID-19 Impact Assessment

A global COVID-19 impact assessment will be used to evaluate the impact of the coronavirus disease pandemic on the severity of the subject's GAD during the last 1 week. The rating will include scores from 0 (not applicable, subject not enrolled in the trial during the pandemic) to 7 (extreme impact). Raters will also evaluate whether the impact was an improvement or worsening of the subject's GAD. The global COVID-19 impact assessment will be completed last after all study assessments by appropriately qualified study center staff and the scores recorded on the eCRF. Every effort should be made to ensure that the assessments are completed by the same assessor at each visit.

CONFIDENTIAL

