To examine the consistency of the primary efficacy results across study centers, the treatment differences versus placebo treatment groups (mean \pm SE) in the change from baseline to Week 8 in PARS severity score, both OC and LOCF, will be graphed by pooled study center.

The comparison of escitalopram vs. placebo will be performed to assess study assay sensitivity.

To assess the impact of COVID-19 on the primary efficacy parameter:

- The primary analysis will be repeated for subjects that were not significantly impacted by COVID-19 (Global COVID-19 Impact Assessment score of 4 or higher, regardless of direction of impact; see section 9.2.5).
- A sensitivity analysis will be conducted by treating remote visits as missing, and analyzing the remaining data using the primary MMRM model.
- A sensitivity analysis will be conducted by repeating the primary analysis and adding the following to the model: an indicator of whether data was collected before or on and after the start of the pandemic (17 March 2020) and the indicator by treatment interaction.
- A subgroup analysis will be conducted by repeating the primary analysis for randomized patients before or on and after the start of the COVID-19 pandemic (17 March 2020).

The subject-level PARS scores will be listed

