9.2.8 Analysis of COVID-19 impact assessment score

The global COVID-19 impact assessment will be used to evaluate the impact of the coronavirus disease pandemic on the severity of the subject's GAD during the last 1 week. The rating will include scores from 0 (not applicable, subject not enrolled in the trial during the pandemic) to 7 (extreme impact). Raters will also evaluate whether the impact was an improvement or worsening of the subject's GAD.

Subjects with scores from 4 (moderate impact) to 7 (extreme impact) at any visit other than the Screening Visit will be considered to have been significantly impacted, regardless of the direction of impact.

Number and percentage of subjects with each score on the global COVID-19 impact assessment will be summarized descriptively at each visit by treatment group for the mITT population, including subjects that were significantly impacted. For each score from 2 to 7, the number and percentage of subjects who improved or worsened will also be summarized.

Page 29 of 53

Page 30 of 53

10.0 SAFETY ANALYSES

The safety analysis will be performed for the double-blind acute treatment period and the double-blind down-taper period separately, using the Safety Population unless stated otherwise.

The safety parameters include adverse events (AEs), clinical laboratory parameters, vital signs, electrocardiographic (ECG) parameters, and suicide risk assessment using the Columbia-Suicide Severity Rating Scale (C-SSRS). For each safety parameter, the last non-missing safety assessment before the first dose of double-blind investigational product will be used as baseline. Continuous variables will be summarized by number of subjects and mean, SD, median, minimum, and maximum values. Categorical variables will be summarized by number and percentage of subjects.

Safety data collected outside of planned visit windows but within allowance limits (up to 1 week late for Visits 7 and 8) will be included in the summary tables. Safety data collected outside of planned visit windows and outside of the allowance limits (>1 week to 6 weeks late for Visits 7 and 8) will be listed, but will not be included in the summary tables. Subgroup analyses may be performed to assess the impact of COVID-19 on the safety analyses; details are listed in each safety section.

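### The COVID-19 sensitivity analysis that drops impacted subjects selects on mostly post-dose ratings of GAD severity, so its estimate can be biased; the defining parenthesis also needs correcting

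*SAP*

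**What the plan says.** SAP 9.1.2 lists four analyses of the pandemic's effect on the primary result. The first is "The primary analysis will be repeated for subjects that were not significantly impacted by COVID-19 (Global COVID-19 Impact Assessment score of 4 or higher"; the parenthesis goes on to disregard direction and to cite section 9.2.5. The other three treat remote visits as missing, add a pandemic-period indicator with its treatment interaction, and split subjects by randomization date at 17 March 2020.

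The definition is in SAP 9.2.8, not 9.2.5, which is the CGI-S summary. It covers "Subjects with scores from 4 (moderate impact) to 7 (extreme impact) at any visit other than the Screening Visit", and these subjects "will be considered to have been significantly impacted, regardless of the direction of impact".

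The instrument is used "to evaluate the impact of the coronavirus disease pandemic on the severity of the subject's GAD during the last 1 week" (SAP 9.2.8, and likewise Protocol 10.1.1.4). On timing, Protocol 10.1.1.4 says: "The global COVID-19 impact assessment will be completed last after all study assessments by appropriately qualified study center staff".

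**The concern.** A subset of a randomized trial stays a randomized comparison if it is defined by something fixed before treatment. This one is not. A single high rating at any point up to Week 8 removes the subject, and the rater is asked about the severity of the same condition that the PARS measures, after completing the PARS. If the rating partly reflects how the child is doing, and treatment changes how the child is doing, the exclusion conditions on a consequence of treatment.

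At stake is how this analysis is read. It is the only one of the four that uses the impact score. If its estimate differs from the primary one, an effect of the pandemic cannot be separated from an effect of selection. Separately, the parenthesis places the threshold for impacted subjects directly after the words for subjects who were not impacted, and points to the wrong section.

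**Working it through.** **Inputs from the documents.** Difference 2.30, SD 5.79, 128 per arm, correlation 0.7, dropout 14%, power 85% (Protocol 11.9, SAP 14.0); 115 evaluable per arm (Protocol 8.3.1); two-sided alpha 0.05; post-baseline PARS at Weeks 2 and 8 only (SAP 3.2).

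**Inputs not given, so assumed.** The share of subjects flagged, and the link between rating and outcome.

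1. *The plan's own figure.* SE = 5.79 × √(2/n); power = Φ(2.30/SE − 1.96).
   - n = 115: SE = 0.764, 2.30/0.764 = 3.01, power 85.4%.
   - n = 128 × 0.86 = 110: SE = 0.780, ratio 2.95, power 83.8%.
   - Crediting Week 2 data, variance per arm = SD² × (0.7²/n at Week 2 + (1 − 0.7²)/n at Week 8), which gives 83.8% to 86.3% depending on when dropouts leave.

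   The stated 85% is reproduced, and the subset rule does not touch it.

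2. *Which ratings count.* The in-clinic schedule lists the form at Screening, Baseline and Weeks 1, 2, 4, 6 and 8. Without Screening, six ratings count, of which five are post-dose. The Baseline rating precedes the first dose, because study drug is dispensed only after the Baseline procedures (Protocol 9.1.2). The remote schedule also lists the form at Week 9. Read literally, a rating made after the endpoint could therefore exclude a subject seen remotely.

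3. *Size under assumed links.* Model: rating = link × standardized PARS change + independent stress, at all six scheduled visits, with the threshold set so that 30% of subjects are flagged and links of 0.3 to 0.7.

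| Analysis | Estimated difference (true 2.30) | Week 8 scores kept |
|---|---|---|
| Planned any-visit subset | 1.84 to 2.23 | 70% |
| All subjects kept, PARS missing only at visits rated 4 or higher | 2.04 to 2.27 | about 91% |
| Subset by Baseline rating only | no bias | not computed |

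4. *A different assumed model.* Here the probability of being flagged depends on Week 8 change alone, with log-odds of 0.5 or 1.0 per SD.
   - Flag unrelated to outcome, or related only to prognosis that treatment does not alter: 2.29 to 2.31, no bias beyond simulation error.
   - Worse outcomes, or better outcomes, flagged more often (18% to 50% of an arm flagged): 1.92 to 2.22. Losses then differ by arm, for example 23.7% of placebo against 18.0% of escitalopram.
   - Large change in either direction flagged (27% to 59% flagged): 1.41 to 2.03, with equal losses in the two arms. Similar exclusion rates would therefore not rule bias out.
   - No true effect: estimate 0 and one-sided rejection about 2.5% throughout.

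5. *Precision.* Removing 30% without any bias leaves 110 × 0.7 = 77 completers per arm: SE = 5.79 × √(2/77) = 0.93, power about 69%.

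**The case against.** The form asks raters to attribute change to the pandemic, not to rate current anxiety, and raters are blinded (Protocol 8.4.7). A link with treatment response is therefore an inference, not something the documents state. That stands, and it is why the conclusion is conditional. Blinding prevents rating by known arm; it does not stop a rating from following symptoms that treatment changes.

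The stakes are limited. This is one of four COVID-19 analyses, and the randomization-date split uses nothing measured after randomization. A bias of 0.1 to 0.4 points is small beside a subset SE of 0.93, and in every scenario with a link it moved the estimate toward zero. All of this stands.

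The visit-level alternative is not clean either. If the rating follows the current PARS score, deleting that score is missing not at random, and the MMRM does not correct it. Under a simpler rating model, with links of 0.3, 0.5 and 0.7, it gave 2.26, 2.09 and 1.99 against 2.23, 2.06 and 1.96 for the subset, almost no gain. Its advantage appears when all six scheduled ratings are modeled, because a high score at Week 1, 4 or 6 then no longer discards a subject's PARS data. The remote-visit analysis is only a partial precedent, since remote visits depend on local restrictions (Protocol 8.2.2.1) and not on a symptom rating.

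A Baseline-defined subset may exclude few subjects, because exclusion criterion 23 already bars those likely to be significantly impacted. That also stands.

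**Conclusion.** The selection rule is a real weakness of one sensitivity analysis. The any-visit subset is not protected by randomization, and its estimate can be biased if the rating tracks treatment response. With 30% flagged and links of 0.3 to 0.7, both assumed, the difference falls from 2.30 to about 1.8 to 2.2. It can fall further if large changes in either direction trigger the flag in a larger share of subjects. The true size cannot be determined from the documents.

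A reader might infer more, and the documents do not support it:
- That the subset estimate is certainly biased. Neither the flag rate nor the link is given, and without a link the bias is zero.
- That the analysis could produce a false positive result. No type I error inflation was found where the flag depends on treatment only through outcome.
- That the primary result, its power or the whole COVID-19 assessment is compromised. None of the primary analysis or the other three COVID-19 analyses uses this rule.
- That the SAP intends to analyze the impacted subjects. The governing words in 9.1.2 and the definition in 9.2.8 make the intent clear; the parenthesis is a drafting error that could mislead a programmer.

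**What to change.** 1. In SAP 9.1.2, reword the parenthesis so that a score of 4 or higher defines the impacted subjects who are excluded, and cite 9.2.8 instead of 9.2.5.
2. Replace whole-subject removal with the primary MMRM in all mITT subjects, setting to missing only the PARS scores at visits (Week 2, Week 8) rated 4 or higher. State that this relies on missing at random, so it reduces the bias but does not remove it, and state that ratings at Weeks 1, 4 and 6 delete no PARS score.
3. Where a randomization-protected subset is wanted, define it by the pre-dose Baseline rating. Note that it ignores later impact and may exclude few subjects because of exclusion criterion 23, and say how a subject without a Baseline rating is classed.
4. If the any-visit subset is kept, label it descriptive, limit it to ratings up to Week 8, and report flag rates by arm and visit.

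The cost is SAP wording and one re-specified sensitivity run. The downside is that the Baseline subset does not address later impact, and the visit-level analysis addresses it only under its stated assumption.
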